STUDY TITLE:

Testing the impact of the PROACTIVE parent program with the caregivers of youth in the child welfare system

PRINCIPAL INVESTIGATOR:

Name: [name]

Department: Psychiatry and Behavioral Sciences

CO-INVESTIGATORS:

Name: [name]

Department: Psychiatry and Behavioral Sciences

VERSION DATE:

12/08/2021

1.0 Purpose and rationale of the study:

Over 650,000 children experience abuse each year in the U.S¹. Approximately 1 in 2 children who experience abuse exhibit mental health symptoms, maladaptive behaviors, and psychiatric disorders². Only about 25% of child abuse victims access mental health treatment; for those who do access treatment, the average time between the first episode of mental disorder and the first treatment contact is over 11 years². Foster parents (referred to as parents below) may not know how to identify their foster child's mental health (MH) needs, find evidence-based MH treatment, or maintain an environment that supports their youth's mental health needs. This is particularly true for children who have special health care needs, as these additional needs increase the

¹ U.S. Department of Health & Human Services, Administration for Children and Families, Administration on Children, Youth and Families, Children's Bureau. (2020). *Child Maltreatment 2018*. Available from <https://www.acf.hhs.gov/cb/research-data-technology/statistics-research/child-maltreatment>.

² Burns, B. J., Phillips, S. D., Wagner, H. R., Barth, R. P., Kolko, D. J., Campbell, Y., & Landsverk, J. (2004). Mental health need and access to mental health services by youths involved with child welfare: A national survey. *Journal of the American Academy of Child & Adolescent Psychiatry*, 43(8), 960-970. doi:<https://doi.org/10.1097/01.chi.0000127590.95585.65>

Farmer, E. M., Mustillo, S. A., Wagner, H. R., Burns, B. J., Kolko, D. J., Barth, R. P., & Leslie, L. K. (2010). Service use and multi-sector use for mental health problems by youth in contact with child welfare. *Children and Youth Services Review*, 32(6), 815-821.

American Psychiatric Association. (2013). *Diagnostic and statistical manual of mental disorders* (5th ed.). Arlington, VA: Author.

In addition to creating the infrastructure and content necessary to support PROACTIVE Parent, this study ultimately has two aims:

1. Does the PROACTIVE Parent Program improve foster parents' capacity for supporting their youth in care's mental wellbeing?
2. Does the PROACTIVE Parent Program improve youth in cares' mental health symptoms, as reported by the foster parents?

2.0 Enrollment Criteria (who can be in your study and who would not be eligible to participate in your study):

For the needs assessment, eligible participants are foster parents of youth with a special health care need (including disabilities, mental health needs, and/or complex medical needs). Participants must be over the age of 18 and be actively fostering a child through the Illinois Department of Children and Family Services.

For the pilot study, eligible participants are foster parents of youth with identified mental health needs. Foster parents must be over the age of 18 and be actively fostering a child ages 5-13 through a child welfare agency in the United States. All participants will also need to speak English, be a resident of Illinois, and be able to navigate virtual meeting technologies (e.g. Zoom).

3.0 Sample Size:

For our needs assessment, we anticipate that 1000 caregivers involved in the specialized foster care program will complete our survey. Given that over 3000 caregivers foster youth in care with special health care needs, we believe that this is a feasible number with recruitment support from DCFS.

For our initial pilot study, we will be recruiting 50 caregivers who will receive the pilot intervention. This pilot data will be used to inform a larger iteration of the study, but we believe that 50 caregivers is sufficient for our initial pilot.

4.0 Recruitment and Screening Methods:

For our needs assessment, we will obtain a list of caregivers involved with the specialized foster care program in DCFS as well as their contact information through the data sharing agreement in place between DCFS and Northwestern. We will attempt to recruit families through email first, then following up with a call, and then sending the survey and recruitment materials to the home. If we are not able to reach the caregivers, we will reach out to the youth's caseworker to facilitate our connection with the caregiver. For families we know do not easily engage with email, we will focus our recruitment efforts on calling and sending mail. Caregivers will be allowed to respond in any way that meets their needs.

For our pilot study, we will work with the Medical Director and the Psychology & Psychiatry Assistant Program Administrator at DCFS to identify caregivers who they believe could benefit from this program as well as organizations that serve foster parents who could connect us to interested families. Once these families have been identified and their contact information has been received by DCFS staff, we will reach out to the caregivers via phone, email, or text to see if they would be interested in participating in this pilot program. If they are interested, a member of the research team will meet with the family via phone or video-based conferencing to discuss the program and to obtain consent. This meeting will also be used to ensure that the family can participate in the intervention. If any of the initial families do not want to participate, or if they are found to be ineligible, we will work with DCFS staff to identify additional families who meet the criteria until we have achieved our desired sample size. Additionally, we will post recruitment information on social media online platforms (Facebook, Reddit, Craigslist, etc.). Potential subjects will be asked to complete a screening questionnaire via REDCap survey that goes over the eligibility criteria for our study. Potential subjects will also be asked to provide us with their contact information at the end of the screening questionnaire (name, email address/phone number).

5.0 Research Locations:

All study interventions will take place virtually. Study staff will meet with participants via Zoom, all data will be collected via REDCap, and data will be converted into reports to share with caregivers. All software used will be part of Northwestern's resources.

6.0 Multi-site Research (research that involves external collaborating institutions and individuals):

All research interventions will be conducted by Northwestern employees and students. However, DCFS staff will assist with recruitment of participants. Since they will only be referring participants to us and will not be participating in any research processes, including collecting consent, the research team believes that IRB approval within DCFS is not warranted.

7.0 International Research (where data collection will occur outside the United States and U.S. territories, including online activities)

This section is not applicable.

8.0 Procedures Involved:

Please check the boxes for all applicable data collection procedures you plan to use:

- One-on-one interviews
- Focus Groups
- Questionnaires/surveys
- Analysis of secondary data (medical record data, educational records, government or private sector datasets, etc.)
- Ethnographic observation
- Physiological measurements (e.g., EEG, EKG, MRI)
- Biospecimen collection (saliva samples, blood draws, hair samples, etc.)
- Mobile applications/data collection devices (e.g., Fitbits, actigraphs, etc.)
- Behavioral decisionmaking tasks (e.g., puzzles, interactive games, etc.)
- Physical activities such as walking and other forms of exercise
- Other procedures (briefly list types of procedures here if not covered by the check-boxes above): _____

This current study has two components that will happen concurrently to iteratively inform the development of the PROACTIVE Parent intervention.

First, the research team will conduct a needs assessment with caregivers of youth in the DCFS specialized foster care program. We will disseminate this 10-15 minute needs assessment using email, online communications, connections with caseworkers, and

mailing hard copies of the survey to families to complete on their own time. This assessment will inform content development for PROACTIVE Parent. It is intended to identify any gaps in services, particularly in regards to mental health services, that will be important for informing the work of future iterations of the PROACTIVE Parent educational program. Parents will be recruited through DCFS and will not be compensated for their time. However, in order to make sure that the assessment is accessible to a wide array of foster parents, we will first pilot the needs assessment with 10 parents in an interview format. These 10 parents will be compensated \$20 for their time.

At the same time, the research team will pilot the initial iteration of the PROACTIVE parent model with foster parents of youth in the foster care programs. After foster parents complete an initial screening via REDCap survey, a member of the research team will contact the foster parent to confirm eligibility. The research team member will then obtain informed consent. After consent has been given, the foster parents will be asked to complete an initial and final assessment. Initial assessment is completed prior to attendance of parent coach sessions and the final assessment is completed after the last session.

The subjects will complete a demographics questionnaire (i.e. name, age, sex, gender, race, ethnicity, education, employment, socioeconomic status, address (for mailing payment, confirmation of state residency, and mailing consent form if requested), caseworker contact information) as part of their initial assessment. We will also ask subjects questions regarding their own parenting needs, their youth's mental health needs, and the parents' ability for engaging with mental health services.

During this initial and final assessment, the parent will complete the following measures:

- Parent-Patient Activation Measure – Mental Health
- PROMIS Parent Proxy Measure – Anxiety
- PROMIS Parent Proxy Measure – Depression
- Pediatric Symptom Checklist-17 (Parent Proxy)
- Barriers to Treatment Participation Scale
- Client Satisfaction Questionnaire (final assessment only)

Data will be collected through a REDCap survey.

Parent involvement in the intervention is anticipated to be 30-60 minutes each session (up to 10 sessions) which may occur over the course of up to 12 weeks.

Foster parents will be compensated \$20 after completing the initial assessment *and* attending the initial session. Foster parents will also be compensated \$20 after completing the final assessment. In addition, foster parents will have the ability to earn

continuing education credits necessary for foster parent licensure for completing this program.

Following the initial assessment, the caregiver will meet with a parent coach, who is an internal member of the NU research team, for 30-60 minutes each session. The content of the sessions will consist of one or more of the following:

- 1) introducing the program
- 2) identifying and setting goals
- 3) discussing results of the assessment
- 4) helping parents develop literacy regarding their child(ren)'s mental health needs
- 5) developing skills on locating mental health services using publicly available resources
- 6) developing skills related to Dialectical Behavioral Therapy, Cognitive Behavioral Therapy, and Parent-Child Interaction Therapy.

After each session, parent coaches will also briefly ask parents questions about their experience with the session to further improve the program (i.e. Post Session Evaluation Questionnaire).

Communication between sessions - to remind foster parents of upcoming sessions or to pass along relevant information in between sessions – will be conducted by email and/or by text. All text communication will happen through personal cell phone or Google Voice number. Google Voice number would provide study staff the option to not use their personal cell numbers to communicate with study participants if they are not comfortable doing so.

9.0 Research with Vulnerable Populations (if children are the ONLY vulnerable population you plan to enroll, do NOT complete this section -- instead fill out Appendix A)

This study will work with foster parents of children with special health care needs, including mental health needs. Since this intervention focuses on the foster parents, we do not believe our population of interest would be considered a vulnerable population.

10.0 Incomplete Disclosure or Deception:

This project does not involve incomplete disclosure or deception.

11.0 Consent Process:

For the needs assessment interview, parents will complete the REDCap e-consent process after a research staff member explains the purpose of the interview, the structure of the survey interview, all benefits and risks, as well as security measures, such as privacy protections and resources, if there is a concern. Since this intervention will be taking place virtually, an e-consent process will be used, where record of consent is stored via REDCap, and a copy of the consent form is emailed or mailed to the participants.

For the needs assessment, parents will complete an online consent form before accessing the survey since we will not be requiring parents provide identifying information (in other words, parents have the option to opt into providing identifiable information but are not required to). This consent form will detail the focus of the study, the length it will take to answer the survey, data security measures, and information on who to contact in case there is an issue or concern. Consenting parents will then select “I agree” after reading through the consent form if they would like to participate. Consenting parents will also have the ability to print or save the consent form from the survey if they would like a copy.

For the parents interested in participating in the PROACTIVE Parent pilot study, they will first meet with a research staff member who has been approved to consent participants over the phone or via video-based conferencing. The research staff member will explain the purpose of the study, the structure of the intervention, all benefits and risks, as well as security measures, such as privacy protections and resources if there is a concern. Since this intervention will be taking place virtually, an e-consent process will be used, where record of consent is stored via REDCap, and a copy of the consent form is emailed or mailed to the participants. The member of the research team who is obtaining consent will e-sign on a separate REDCap form to confirm consent was obtained.

12.0 Waiver of Participant Signature on Consent Form:

The initial 10 parents who will be piloting the needs assessment, a waiver of consent is not being requested. Parents will provide an e-signature for consent, using REDCap’s e-consent process, since we will be interviewing them to test the usability of the survey. This consent form can be found under “Needs Assessment Interview Consent.” For the actual needs assessment, though, parents will complete an online consent form. We felt this was appropriate since parents do not have to provide identifying information. This consent form can be found under “Needs Assessment Consent.”

For the pilot component of the study, a waiver of participant signature is not being requested.

13.0 Waivers and Alterations of Consent Information:

Waivers and alterations of consent information are not being requested.

14.0 Financial Compensation:

The first 10 parents who complete the initial needs assessment interview will receive \$20 for their time. Parents who complete the finalized needs assessment will not be compensated.

Parents who participate in the pilot study will receive \$20 after initial assessment is completed *and* attendance of initial session. Participants will also receive \$20 after completing the final assessment. Participants will have the opportunity to earn \$40.

Parents will also be able to receive continuing education credits to maintain their foster parent licensure after completing the PROACTIVE Parent intervention.

Participants will either receive payment in the form of a \$20 gift card or a stored e-gift card.

Participants will be responsible to cover the costs of accessing the needs assessment, talking on the phone or Zoom with research staff either both project, and/or any online resources utilized during the pilot study.

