learning new skills, learning how to locate services for their child, and obtaining referrals to providers through a publicly accessible databases. Thus, while this program fills in gaps in traditional mental health services, it does not constitute comprehensive mental health treatment, a fact that will be consistently emphasized to participants throughout both parts of the study. We will explicitly include this in the consent form and check in with participants regularly to ensure that this is understood and that participants have access to complete services. In addition, parents might feel uncomfortable sharing personal information with research study staff. In order to mitigate this risk, we will emphasize that participants do not have to answer any question they do not want to or participate in any activity that makes them uncomfortable. If they continue to feel uncomfortable, they can choose to opt out of the remainder of the needs assessment or pilot study, depending on which they are enrolled in.

18.0 Provisions to Protect Participant Privacy and Data Confidentiality:

In terms of data storage, all data will be stored on secure Northwestern servers and only accessed by members of the research team. While the data will be stored with identifiers, since the research staff will need to contact participants, data will be de-identified when downloaded. When the data is being transferred from REDCap to the M drive, it will be downloaded on an FSM computer and immediately transferred to the appropriate M drive location. The data will be stored indefinitely on the M drive and on NU's REDCap server.

In terms of delivering the pilot intervention, all coach - participant check-ins will be held using confidential video-based software (e.g. Zoom) and will be conducted in a private setting where others not involved in the research project cannot hear the advocates' conversations with participants.

19.0 Data Monitoring Plan to Ensure the Safety of Participants:

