Cover Page

Study: PROACTIVE Parent: PROviding Access To InnoVative & Evidence-Based Intervention

Date: 6/16/21

Statistical Plan

We plan to enroll 14 foster parents with 7 foster parents per condition.

For the primary outcomes: acceptability, usefulness, and feasibility we will conduct descriptive analyses separately for the post-session items and the post-intervention Customer Satisfaction Survey. We will sum relevant items on the post-session questionnaires (administered after each of the 10 sessions) and provide mean ratings for program Acceptability, Usefulness, and Feasibility. We will provide mean ratings for Acceptability, Usefulness, and Feasibility from the Customer Satisfaction Survey. We will also provide descriptive statistics for other aspects of Feasibility as described below.

For the primary Treatment vs. Control group analyses we will examine 2 (Group) x 2 (Time) repeated measures ANOVA, with repeated measures on the second factor (Time). For measures that include subscales we will use K (number of subscales) x 2 repeated measures MANOVA to assess for treatment effect on subscale scores. For the child outcome measures we will use 2 x 2 repeated measures MANOVA with each of the child outcome measures and/or subscale scores in one model, as the child outcomes may share some variance.

For the delayed treatment analyses, we will combine the treatment and the delayed treatment participants to examine a one-way repeated measures ANOVA examining the pre-post scores of each of the groups – essentially using T1 and T2 data for the original treatment group and the T3 and T4 data for the delayed treatment groups. We will use a one-way repeated measures MANOVA for the child outcomes.

Primary Outcomes. Primary Outcomes will be assessed with three types of measures. Post-session measures that assess session content and delivery at the end of each of the 10 sessions, post-intervention in a Customer Satisfaction Survey, and pre- and post-intervention with standardized measures.

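### The end-of-program satisfaction survey is scheduled only after the last session, with no stated provision for parents who stop early, so its mean will probably describe finishers

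*Protocol*

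**What the plan says.** Protocol section 8.0 (Procedures Involved) lists the measures for the initial and final assessments. One is marked as final only: "Client Satisfaction Questionnaire (final assessment only". On timing, the same section says "the final assessment is completed after the last session". Sessions number at most ten, over at most 12 weeks. Section 8.0 also provides a rating at each session: "After each session, parent coaches will also briefly ask parents questions about their experience with the session".

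Protocol section 17.0 (Potential Risks to Participants) deals with parents who are uncomfortable sharing information. It first says that "participants do not have to answer any question they do not want to or participate in any activity that makes them uncomfortable". For those who remain uncomfortable, it adds that "they can choose to opt out of the remainder of the needs assessment or pilot study".

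The SAP (Statistical Plan) names acceptability, usefulness and feasibility as primary outcomes and summarises two sources separately. For the survey: "We will provide mean ratings for Acceptability, Usefulness, and Feasibility from the Customer Satisfaction Survey". For the session forms: "We will sum relevant items on the post-session questionnaires (administered after each of the 10 sessions". Under Feasibility, the SAP also reports the percentage of parents who finished every study task.

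Neither document describes an exit administration of the survey, an item on why a parent stopped, a denominator for the survey means, or a rule for missing ratings.

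**The concern.** A parent's view of the program can affect whether the parent stays in it. If the only whole-program rating is taken after the last session, parents who leave because the program did not suit them are the ones most likely to be missing from it. The survey has no baseline and no repeat, so a missing survey score cannot be filled in from an earlier value of the same instrument.

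Protocol section 3.0 says the pilot data will inform a larger study. A survey mean drawn mainly from finishers would tell the designers of that study least about the parents whose experience matters most for revising the program. It could also make the program look more acceptable than it is to those who start it.

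**Working it through.** The plan gives no figure to reproduce here: there is no expected stopping rate, no rating SD and no missing-data rule. The check has two parts, a walk through the text and an illustration of size.

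**1. One parent followed through the plan.** Take a parent who attends three sessions and then stops.

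- *Post-session forms (Protocol 8.0; SAP, Acceptability, Utility and Feasibility):* up to three sets of ratings, covering satisfaction, usefulness, relevance, timing and format, with open comments. There are none for later sessions.
- *Satisfaction survey (Protocol 8.0):* not described for this parent, unless the last session is read as the last one attended. The text does not say which is meant.
- *Reason for stopping:* no item is described.
- *Completion percentage (SAP, Feasibility):* the parent counts as a non-completer, which shows neither the reason nor the opinion.

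So the parent does appear in the data, but probably not in the survey mean.

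**2. Why the session forms only partly fill the gap.** They rate a session, not the program as a whole. The coach who delivered the session asks the questions, which may mute criticism. They end when the parent stops, so later-session means come from a shrinking group. The SAP assumes forms after all ten sessions, while the protocol allows fewer. The SAP has no rule for parents with fewer forms, and if items are summed across sessions, totals are not comparable between parents.

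**3. Size of the distortion in the survey mean.** Let p be the share of starters who stop and give no survey rating, F the finishers' mean, S the mean the stoppers would have given, and d = F − S in SD units.

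- Mean over all starters = (1 − p)F + pS
- Finishers' mean minus that = F − (1 − p)F − pS = p(F − S) = p × d

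Assumed ranges are p = 20-40% and d = 0.5-1.0 SD. Sample sizes are 50 (Protocol 3.0) and 14 (SAP).

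| p | p × 0.5 | p × 1.0 | Unrated of 14 | Unrated of 50 |
|---|---|---|---|---|
| 0.20 | 0.10 SD | 0.20 SD | 2.8 | 10 |
| 0.30 | 0.15 SD | 0.30 SD | 4.2 | 15 |
| 0.40 | 0.20 SD | 0.40 SD | 5.6 | 20 |

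The bias in SD units depends on p and d only, so the 14-versus-50 difference between the documents does not change it.

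**4. Chance that at least one rating is missing.** This is 1 − (1 − p)^n. With n = 14:

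- p = 0.10: 1 − 0.9^14 = 0.77
- p = 0.20: 1 − 0.8^14 = 0.96
- p = 0.30: 1 − 0.7^14 = 0.99

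Even modest stopping would very likely leave the survey incomplete at the SAP's sample size.

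**The case against.** The strongest reply is that the plan already hears from stoppers. A reader might infer that parents who stop never rate the program. The documents do not support that: a parent who stops after k sessions can have up to k post-session ratings on the same three constructs, plus comments. Only a parent who leaves before finishing a first session gives none. Early-session ratings of eventual stoppers and finishers could be compared with no new data collection, so the selection can be examined in part. This stands, and it limits the point to the end-of-program survey.

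A reader might also infer that opting out bars a parent from the final assessment. Section 17.0 does not say so. It grants a permission, placed after a right to decline single questions or activities, and it is not a discontinuation rule. The last session may mean the last attended, and the second $20 payment depends only on completing the final assessment. This also stands. What remains is that the plan never states that stoppers are to be approached, and the right to decline an activity is not a stated route for ending coaching while still giving the final rating.

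The completion percentage will show how many did not finish, but not how they rated the program or why they stopped.

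Finally, the size is wholly assumed, including the idea that dissatisfaction drives stopping. If parents stop for reasons unrelated to their opinion, d is near zero and so is the bias. That is a fair limit on the size. A reason-for-stopping item would help settle it.

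**Conclusion.** The point holds for the end-of-program survey. It is scheduled only at the final assessment, it is one of two sources for three primary outcomes, and neither document provides for giving it to parents who stop early. Its mean will therefore most likely describe finishers. If 20-40% stop and would rate 0.5-1.0 SD lower, the mean is 0.10-0.40 SD too favourable. Both ranges are assumptions, and the figure does not apply to the post-session ratings.

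The conclusion also rests on two readings. One is that the protocol's Client Satisfaction Questionnaire and the SAP's Customer Satisfaction Survey are the same instrument, inferred from their matching timing. The other is that staff would take the last session to mean the end of the program. If the sponsor means the last session attended, one sentence saying so removes much of the problem. The consent form was not available for this review, so its wording on stopping could not be checked.

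This is a cheap improvement worth making before data collection, because a survey rating not sought at exit cannot be recovered later. It does not invalidate the pilot.

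**What to change.** - **Protocol 8.0:** state that the final assessment follows the last session attended. Send the existing satisfaction survey by REDCap link, with one voluntary item on the main reason for stopping, to every parent who attended at least one session and stops early. Use one name for the instrument in both documents.
- **Protocol 17.0 and consent form:** distinguish ending sessions while still completing assessments from leaving the study altogether, with both voluntary. This concerns data collection only.
- **SAP, survey:** report means with the number responding out of all who started sessions, separately for finishers and stoppers.
- **SAP, post-session forms:** summarise ratings by session number with the number of parents contributing, and compare the early-session ratings of stoppers and finishers.

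The cost is a second trigger for an existing survey, one added item, and wording in the protocol, consent form and SAP. Some stoppers will not answer, so the gap narrows but does not close, and the reported mean is likely to be less favourable.

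### Parent coaches ask the post-session questionnaire and no private completion is described, so the post-session means, chiefly for acceptability and utility, risk a courtesy bias, probably upward and of unknown size

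*Protocol*

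**What the plan says.** **Who asks.** Protocol 8.0 (Procedures Involved) says of the Post Session Evaluation Questionnaire: "After each session, parent coaches will also briefly ask parents questions about their experience with the session to further improve the program". The same section says that "the caregiver will meet with a parent coach, who is an internal member of the NU research team".

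**How data are captured.** Protocol 5.0 (Research Locations) states: "Study staff will meet with participants via Zoom, all data will be collected via REDCap". In 8.0, the measures of the initial and final assessments are listed as completed by the parent, followed by "Data will be collected through a REDCap survey". The end-of-program satisfaction questionnaire is on that list, at the final assessment only. The post-session questionnaire is not on it.

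**How the ratings are used.** The SAP, under Primary Outcomes, includes "Post-session measures that assess session content and delivery at the end of each of the 10 sessions". Its Statistical Plan says "we will conduct descriptive analyses separately for the post-session items and the post-intervention Customer Satisfaction Survey". Acceptability covers satisfaction, likes and wished-for changes. Utility covers usefulness and relevance. Feasibility covers timing and format, and adds coach adherence and eligibility, enrolment and completion percentages. Neither document sets a benchmark or progression threshold for any of these ratings.

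**Which design.** The SAP (6/16/21) states: "We plan to enroll 14 foster parents with 7 foster parents per condition". The protocol (12/08/2021), section 3.0, plans 50 caregivers, all receiving the intervention, and does not name these ratings as outcomes.

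**The concern.** A parent asked by a coach to rate a session has a social reason to be kind. Acceptability and utility items judge the session directly, so they are the most exposed. Timing and format are less personal, and adherence and enrolment figures are not parent ratings at all.

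The post-session means are uncontrolled. A courtesy shift is therefore not cancelled by a comparison group and is not reduced by recruiting more parents. Two uses are at stake: the description of how the program was received, and the protocol's own aim of improving it, which depends on candid criticism. The open-ended items give parents room to criticise, but they belong to the same post-session assessment and share its mode.

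**Working it through.** There is no figure in the plan to reproduce: the documents give no rating scale, SD, target or threshold for these items. The check is mainly a reading of the text, with limited arithmetic for scale.

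**1. Does any statement provide private completion?**
- Protocol 8.0: coaches ask. The natural reading is the coach who gave the session, though the text does not say so outright.
- Protocol 5.0: REDCap holds all data. This names the platform, not who enters the answers or who can see them. A coach could ask aloud and type.
- Protocol 8.0, initial and final assessments: parent-completed, by REDCap survey. The post-session form is outside that list.
- Protocol 18.0: coach check-ins take place in a private setting. This keeps out people who are not on the project, not the coach.

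So private completion is not described, and the one stated procedure is that coaches ask.

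**2. Forms exposed, at most.**
- SAP: 14 parents × 10 sessions = 140, counting the delayed-treatment group.
- Protocol: 50 caregivers × up to 10 sessions = 500.

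These are ceilings on forms asked by coaches, not counts of biased answers.

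**3. What a constant shift does to the mean.** If each rating is raised by b, the observed mean is the true mean + b, whatever the number of parents. Averaging over sessions leaves b unchanged. The random error does shrink: with one mean per parent and independent parents, the standard error in between-parent SD units is 1/√n.
- n = 14: 1/√14 = 0.27
- n = 50: 1/√50 = 0.14

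The ratio of shift to standard error is b√n. The documents give no value of b, so the range below is an assumption for illustration, not a finding about this trial. Coverage is that of a nominal 95% t-interval for normal data, from the noncentral t distribution with noncentrality b√n.

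| Assumed b (SD) | b√n, n = 14 | Coverage, n = 14 | b√n, n = 50 | Coverage, n = 50 |
|---|---|---|---|---|
| 0.1 | 0.37 | 93.6% | 0.71 | 89.3% |
| 0.2 | 0.75 | 89.3% | 1.41 | 71.6% |
| 0.3 | 1.12 | 82.0% | 2.12 | 45.2% |
| 0.5 | 1.87 | 59.0% | 3.54 | 6.6% |

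With 14 parents, a small shift is of the same order as sampling error or below it. With 50, the same shift stands out more. The table shows how sample size interacts with a bias; it does not show that a bias exists.

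**The case against.** **Two documents are being joined.** Coach asking appears only in the later protocol, which gives program improvement as the purpose. Primary status appears only in the earlier SAP, which does not say who administers the form. Under the protocol alone, this is formative feedback, and a coach's brief question is an ordinary way to gather it. This stands, and it limits the weight of the point. The mode problem itself does not depend on the label.

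**The mode is unspecified, not shown to be faulty.** Asking does not exclude sending a link. A reader might infer that private completion is ruled out, or that the ratings are in fact inflated. The documents support neither: they are silent on who enters the answers, and the upward direction is a methodological inference. Even so, the procedure as written can be followed to the letter with the coach asking face to face, so this is more than a missing detail.

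**There is a second source.** The SAP takes mean acceptability, usefulness and feasibility from the satisfaction survey as well, and the protocol collects its satisfaction questionnaire by REDCap survey at the final assessment. (I take the differently named instruments to be the same.) A reader might infer that a courtesy shift could never be noticed, but a gap between the two sets of ratings would be a visible, imperfect signal. It is imperfect because timing and content differ as well as mode.

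**The remedy has its own bias.** Unpaid forms completed alone may go missing selectively, and a completion count shows how many are missing, not in which direction that pulls the mean. Up to 10 such forms could also lower the SAP feasibility percentage for completing all study tasks, if they count as tasks. Both points stand and are dealt with in the fix.

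**Conclusion.** The point holds as a risk. The stated procedure has coaches ask for ratings of the sessions, no private completion is described, and the resulting uncontrolled means are open to a courtesy bias, probably upward, chiefly for acceptability and utility. Its size cannot be estimated; only the ceilings of 140 or 500 exposed forms follow from the documents.

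The consequence is limited. No threshold, test or stated decision depends on these ratings, and the final satisfaction questionnaire is a partial check. A reader might infer that the SAP's primary outcomes as a whole are compromised. They are not: the group comparisons on standardized measures and the adherence and enrolment figures do not use these ratings. The change is worth making because it is cheap and improves both the description of the program and the feedback used to refine it.

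The conclusion rests on three assumptions: that coaches ask in person, as the text naturally reads; that parents soften criticism in that setting; and that the ratings keep a reporting role under the later protocol, which the sponsor should confirm.

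**What to change.** **Change Protocol 8.0** so that the parent completes the Post Session Evaluation Questionnaire alone, through a REDCap link at the close of each session. Tell the parent that the coach does not see individual answers during the program, and that another existing team member reads the open text, so that the monitoring in Protocol 19.0 is kept.

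**Add to the SAP:**
- the number of forms completed out of sessions attended;
- the post-session means set beside the final satisfaction ratings, described as an imperfect check on mode;
- post-session form completion reported separately from the feasibility percentage for completing all study tasks;
- confirmation of whether these ratings are primary under the current protocol.

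If parents already complete the form privately, one sentence saying so replaces the procedural change.

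**Cost.** One form on the platform already in use, a few lines of text, and staff time to read open answers. The downside is some non-response, possibly selective, since Protocol 14.0 ties payment to the initial assessment with the first session and to the final assessment, not to these forms. The coach also receives less direct spoken feedback.
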